Resting energy expenditure (EE) comprises 60-75% of the total EE in an average adult human. Resting EE is not static. Like other mammals, humans adjust EE (or heat production) to balance heat loss in order to maintain constant body temperature. In rodents, the relationship between EE and environmental temperature is shown graphically in figure 1. In an ongoing protocol (12-DK-0097), we are mapping this response in men and women to determine the effect of adiposity, age, and race on the response to a short-term and tolerable temperature manipulation.

Animals invoke physiological adaptations such as vasoconstriction and piloerection in response to the changing ambient temperature. The temperature range at which such adaptations are sufficient to maintain a minimum heat production to balance the heat loss is called a thermoneutral zone (TNZ).^{1,2} Within the TNZ, resting EE is known as basal metabolic rate (BMR). When these responses cannot sufficiently compensate for the increased heat loss associated with the further decrease in ambient temperature, additional EE is needed. Figure 1 shows this thermogenic response process is gradual which reflects the net heat balance of the animal. Moreover, when exposed to extreme cold, muscle shivering is recruited to increase heat production, but cannot be maintained for a prolonged period of time. In contrast, exposure to mild cold induces non-shivering thermogenesis (NST),³ which may be sustainable and tolerable. NST has been studied to a limited extent in adult humans, with high variability in its estimates due to several potential factors (Table 1).

[figure not shown]

Figure 1. Graphs of the metabolic rate (oxygen consumption) vs environmental temperature relationships, Figures 1 and 4 in Cannon and Nedergaard¹. BMR is basal metabolic rate (also known as resting EE in humans).

One source of variability is the actual definition of NST used in the studies. NST is the % change in resting EE at a defined cold temperature without shivering as compared to the BMR measured at thermoneutrality (within the TNZ). Individual TNZ is

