variable, for which traditional measurements of resting EE (not the true BMR) often do not carefully control for this factor. The second cause may be the differences in testing conditions, including the ambient temperature used for cold exposure and the insulating properties of the clothing worn during testing (quantified by a commonly used term clo for measuring the thermal insulation of clothes, where zero [0] Clo corresponds to a naked person and one [1] Clo corresponds to a person wearing a typical business suit.) Other sources of variability in NST include food intake, posture and physical activity (Table 1) during the testing period.

It was recently rediscovered that brown adipose tissue (BAT) is functional in adult humans⁴⁻⁷ and its presence and activity appear to be highly variable. The primary function of BAT is to maintain body temperature and may be an important contributor to NST. BAT releases the energy from substrate oxidation as heat via uncoupling protein 1 (UCP1), rather than using the energy to generate ATP⁸. Moreover, non-shivering heat generation may also occur in skeletal muscle, through browning of white adipose tissue, and by other factors that contribute to the high variability of the cold-induced thermogenesis in the literature. Taken together, there is great interest in understanding the underlying mechanisms governing NST contribution to total body energy homeostasis and body weight regulation. Understanding these control mechanisms will provide insight into the pathophysiology underlying the current epidemic of obesity and should provide insight into potential treatments.

Table 1. A brief summary of literature review of cold-induced thermogenesis.

% Increase	Metric	Temp range, C	Clo	Reference
7.0	24h resting	22-28	NA	Dauncey MJ (1981) ⁹
11.0	day resting	22-28	NA	Dauncey MJ (1981) ⁹
6.0	24h resting	16-22	0.71	van Marken Lichtenbelt (2002) ¹⁰
4.9	24h resting	16-22	0.71-0.8	Wijers SL (2007) ¹¹
6.0	day resting	19-24	0.55	Celi FS (2010) ¹²
3.5	day resting	16-22	0.8	Wijers SL (2011) ¹³
For comparison:				
17.4	day resting	18-27	0.36	12-DK-0097, preliminary analysis

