Within the scope of protocol 12-DK-0097, while defining the detailed relationship between resting EE and environmental temperature, we are defining the maximum amplitude or the capacity of NST. In brief, in that protocol the range of environmental temperatures being studied (16-31°C) is that routinely encountered during daily activity, including the comfort zone¹⁴ and slightly lower. Importantly, the protocol is designed to minimize the contributions of physical activity, thermic effect of food, and behavioral changes (such as changes in body position) and standardizes the insulating properties of clothing worn for testing (clo=0.36). Thus the measured EE is expected to reflect NST in response to the environment. The protocol determines the following parameters

experimentally (see Figure 1^{1,15}): 1) the thermoneutral zone (TNZ), defined as the environmental temperature range in which EE is at a minimum and does not change with environmental temperature, 2) the shivering threshold, defined as the lowest environmental temperature before shivering occurs, and 3) the capacity for non-shivering thermogenesis, defined as the difference in EE measured at the shivering threshold and at thermoneutrality.

To our knowledge, 12-DK-0097 is providing the first rigorous measurement of the capacity for non-shivering thermogenesis in humans. In a preliminary analysis of the first subjects, a lean Caucasian cohort, EE at the shivering threshold was $17.4 \pm 3.7\%$ ($n=6$) greater than BMR. We were initially surprised by this unexpectedly large capacity for non-shivering thermogenesis, as prior publications of mild cold-induced thermogenesis found increases of only 3 to 11% (Table 1). However, we believe that the 17% value as seen in our current study is plausible for the following reasons: 1) our measurements are in the fasting state, removing any masking of facultative thermogenesis by the thermic effect of food (a phenomenon already recognized by Rubner in 1902⁹), 2) strict enforcement of no physical activity, 3) strict prohibition of postural and behavioral changes, and 4) actual measurement of the TNZ and shivering threshold, ensuring that the full span of NST is captured, compared to two fixed temperature points which were used by most previous studies. We note that a crucial innovation is the use of a relatively short time period for the EE measurements, allowing stricter control of the above variables, enabled by specialized analysis of the chamber data¹⁶.

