The principal physiologic stimulus to BAT (and possibly muscle for NST) is via the sympathetic nervous system (SNS). When activated, sympathetic nerves release norepinephrine which binds to α - and β -adrenergic receptors on adipocytes to stimulate heat production, with the β -adrenergic receptors driving thermogenesis. Indeed there are clinical reports that the β -adrenergic receptor blocker propranolol reduces the uptake into BAT during FDG-PET studies by 55 to 75%^{25,26}. While adipose tissue shares β 1- and β 2-adrenergic receptors with many tissues, the tissue distribution of β 3-adrenergic receptors is restricted and thus β 3-adrenergic agonists could be used to selectively target adipose tissue, as is done in preclinical studies (eg²⁷). However, the β -adrenergic receptors on adipose tissue do not appear to be interchangeable. While β 3-receptors are typically assumed to be the major driver, β 2-adrenergic receptors alone are sufficient for normal BAT morphology²⁸ and the β 1-adrenergic receptor has been reported to be able to mediate most of the sympathetic stimulation of cold-induced thermogenesis²⁹. α 1-adrenergic agonists can also augment BAT stimulation, but do not contribute in the absence of β -adrenergic stimulation³⁰.

While the molecular details of muscle NST are not clear, it appears that in mice, dantrolene, via inhibition of the ryanodine receptor calcium channel, RyR1, can inhibit

muscle NST²⁴. Thus, dantrolene is a unique tool that may allow distinguishing of muscle vs BAT sources of NST.

In this protocol we will focus on the regulatory pathways of human NST via pharmacological modulations of the SNS receptors. The results of these studies will allow us to elucidate the receptors controlling NST in humans, and by inference, the contribution of BAT.

Propranolol

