The effect of 160 mg propranolol at thermoneutrality is expected to be slight. Propranolol's effect on EE has been studied multiple times, with three examples being a reduction of 4.1% (non-significant³⁵), 1.6% (non-significant³⁶), and 5.0% (p=0.002¹¹). At the low temperature, 160 mg should have a proportionally greater effect on reducing EE, although any prediction of the magnitude is largely an estimate.

Pindolol

A complementary test of the drivers of NST would be use of a selective β 3-adrenergic agonist³⁷, but none is currently approved for this use in humans. However, pindolol (Visken, label: http://www.accessdata.fda.gov/drugsatfda_docs/label/2007/018285s034lbl.pdf) is an

approved drug with properties suitable for ‘clamping’ the β -adrenergic tone. Pindolol is a mixed partial agonist and antagonist. At complete receptor occupancy, a partial agonist gives less response than that of the native ligand. In the presence of a full agonist, saturating partial agonist will reduce the receptor response.

Pindolol has pharmacokinetic and binding properties indicating that full receptor occupancy can be achieved with single oral dosing in humans. Specifically, pindolol has binding K_{iS} of 2.6, 4.8, and 44.1 nM for the human $\beta 1$ -, $\beta 2$ -, and $\beta 3$ -adrenergic receptors, respectively³¹. The pharmacokinetics of a 20 mg dose of pindolol include a Cmax at ~1-2 hours of ~96 ng/ml, t_{1/2} of ~2.9 hours, and 38% plasma protein binding³⁸. From the total plasma concentration at the Cmax of ~387 nM, one can estimate that the Cmax after a 20 mg dose of pindolol will yield free plasma concentrations that are 92-, 50-, and 5.4-fold the K_{iS} of the $\beta 1$ -, $\beta 2$ -, and $\beta 3$ -adrenergic receptors, respectively. These data indicate that 20 mg of pindolol should saturate all three endogenous β -adrenergic receptors.

Pindolol is an antagonist at $\beta 1$ -adrenergic receptors^{31,39} and a partial agonist at $\beta 3$ -adrenergic receptors^{31,40}. It may either be a partial agonist³⁹ or antagonist³¹ at the $\beta 2$ -adrenergic receptor. Interpreting reports of β -adrenergic receptor selectivity that antedate discovery of the $\beta 3$ -adrenergic receptor and of partial agonism that do not consider biased agonism⁴¹ add some uncertainty. However these are moot, assuming that pindolol saturates all three β -adrenergic receptors.

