If the predominant signaling to human NST mechanisms is via β -adrenergic receptors, one expects that by clamping β -adrenergic tone with pindolol, the same level of change in REE_{Low} and REE_{27°C} will be observed. Since pindolol is a partial agonist, the prediction is that this clamped EE will be elevated moderately at a level between REE_{27°C} and REE_{Low} with placebo.

Dantrolene

To differentiate NST from skeletal muscles, we will use the following two pharmacologic agents. Dantrolene (Dantrium, label:

http://www.accessdata.fda.gov/drugsatfda_docs/label/2012/017443s043s046s048s049lbl.pdf) is clinically indicated for treatment of muscle spasticity⁴² and of malignant hyperthermia⁴³. Dantrolene binds and inhibits the muscle ryanodine receptor (RyR1), which releases calcium from the sarcoplasmic reticulum^{44,45}. A recent study in mice suggests that dantrolene blocks muscle NST, but has no effect on BAT NST²⁴.

Clinical dosing of dantrolene for spasticity is via titration from 25 mg QD to up to 100 mg TID, or even 100 mg QID (label). The pharmacokinetics of a single 100 mg oral dose of dantrolene include a Cmax at ~4.5 hours of 0.7-1.45 ug/ml (2.2-4.6 uM; Mr is 314), and t_{1/2} of 9-12 hours⁴⁶⁻⁴⁸. Single oral doses as high as 150 mg have been reported⁴⁷.

It is not clear what level of dantrolene is needed to maximally inhibit RyR1. Dantrolene is hydrophobic and highly bound to albumin⁴⁹, but we are not aware of any clinical measures of free drug levels. Thus, how an in vitro IC50 of 300 nM⁴⁵ corresponds to the exposure achieved with a single 100 mg oral dose of dantrolene is unknown.

We are not aware of prior studies of the effect of dantrolene on EE under conditions similar to those in this protocol. The prediction is that a single oral 100 mg oral dose of dantrolene will significantly inhibit muscle NST in humans.

Magnesium sulfate

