- 1) Propranolol 160 mg PO will reduce the resting EE measured at a temperature just above the subject's placebo shivering threshold (REE_{Low}) by greater than or equal to 5% compared to placebo REE_{Low} . If propranolol-treated subjects shiver at the low temperature, then measurement of non-shivering EE is not possible in this protocol. Propranolol will be judged to increase the shivering threshold if significantly more subjects shiver with propranolol than with placebo treatment.
- 2) Pindolol 20 mg PO will lead to a similar difference in resting EE measured at thermoneutrality ($REE_{27^\circ C}$) and REE_{Low} .
- 3) Dantrolene 100 mg PO will reduce the REE_{Low} by greater than or equal to 5% compared to placebo REE_{Low} . If dantrolene-treated subjects shiver at the low temperature, then measurement of non-shivering EE is not possible in this protocol. Dantrolene will be judged to increase the shivering threshold if significantly more subjects shiver with dantrolene than with placebo treatment.
- 4) Magnesium sulfate (50 mg/kg bolus followed maintenance infusion at 2 g/h) will reduce the REE_{Low} by greater than or equal to 5% compared to REE_{Low} .

Cohort 2

- 1) To evaluate the effect of caffeine (300 mg PO) on BMR ($=REE_{27^\circ C}$).
- 2) To evaluate the effect of Qsymia (topiramate 92 mg CR, phentermine 15 mg PO) on BMR.

- 3) To evaluate the effect of phentermine (37.5 mg PO) on BMR.
- 4) To evaluate the effect of topiramate (200 mg PO) on BMR.
- 5) To evaluate the effect of naltrexone (100 mg PO) on BMR.

Hypotheses

- 1) Caffeine 300 mg PO will increase BMR by greater than or equal to 5% vs placebo.
- 2) Qsymia (topiramate 92 mg CR, phentermine 15 mg) PO will increase BMR by greater than or equal to 5% vs placebo.
- 3) Phentermine 37.5 mg PO will increase BMR by greater than or equal to 5% vs placebo.
- 4) Topiramate 200 mg PO will increase BMR by greater than or equal to 5% vs placebo.
- 5) Naltrexone 100 mg PO will increase BMR by greater than or equal to 5% vs placebo.

Cohort 3 – This Cohort has completed enrollment

- 1) To compare the effects of mirabegron at 0mg, 50mg, and 200mg on BAT metabolic activity.
- 2) To compare the effects of mirabegron at 0mg, 50mg, and 200mg on BMR.

Hypotheses

- 1) Mirabegron at 50mg and 200mg PO will each increase BMR and BAT activity more than placebo.
- 2) The increases in heart rate and systolic BP after a one-time dose of 50mg will be lower than that observed using 200mg.

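### For propranolol, dantrolene and magnesium, a fall in low-temperature resting EE cannot by itself show NST inhibition; the planned two-temperature contrast that can is not tied to the NST conclusion

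*Combined protocol and SAP*

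**What the plan says.** Section I defines NST in two ways, both relative to thermoneutral EE. The first is relative: "NST is the % change in resting EE at a defined cold temperature without shivering as compared to the BMR measured at thermoneutrality". The second is absolute: "the capacity for non-shivering thermogenesis, defined as the difference in EE measured at the shivering threshold and at thermoneutrality". Section I.2 states the purpose of the drug studies: "The results of these studies will allow us to elucidate the receptors controlling NST in humans". It also predicts that dantrolene and magnesium will inhibit muscle NST.

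The Cohort 1 hypotheses in section II.1 use a different quantity for three of the four drugs. Item 1 reads "Propranolol 160 mg PO will reduce the resting EE measured at a temperature just above" the placebo shivering threshold, by at least 5% against placebo REE_Low. Items 3 (dantrolene) and 4 (magnesium) follow the same pattern. Item 4 omits the word placebo before the comparator, and I read it as placebo. Items 1 and 3 add a rule on shivering, which concerns the shivering threshold and does not use the 27°C value. Item 4 has no such rule. Only pindolol has the difference between the two temperatures as its primary objective.

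Section II.2 lists, as secondary objectives to be reported, the drug-versus-placebo comparison of delta-EE (item 3) and the drug-placebo difference in EE at the same temperature (item 4). Section III.2-1 and Table 4 give placebo and every drug one low-temperature session and one 27°C session.

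**The concern.** Under the protocol's own definitions, REE_Low is thermoneutral EE plus the NST increment. A drug that lowers EE equally at every temperature lowers REE_Low and leaves NST alone. A drug that blocks NST lowers REE_Low and leaves thermoneutral EE alone. The primary comparison gives the same answer for both, yet they are opposite answers to the Cohort 1 question of what drives NST.

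The plan does not say that an NST conclusion needs the two-temperature contrast, and it gives that contrast no hypothesis, criterion or power. A significant REE_Low with an unchanged contrast would meet the primary hypothesis, and nothing in the plan says how that pair of results should be read.

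**Working it through.** **Inputs.** From the power calculation in section III.1: n = 12 completers, true difference 5.0%, SD 2.54% (described as a within-subject difference in BMR), NST 17.4 ± 3.7%, stated power 0.98 at alpha 0.05 and 0.94 at alpha 0.05/4 = 0.0125. Sidedness is not stated; two-sided is assumed.

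**1. The plan's own power.** Paired t-test, df = 11, noncentrality = difference × √12 / SD.

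| SD of the drug-placebo difference | alpha 0.05 | alpha 0.0125 |
|---|---|---|
| 2.54 | >0.999 | 0.999 |
| 2.54 × √2 = 3.59 | 0.992 | 0.946 |
| 3.7 | 0.989 | 0.932 |

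The stated 0.98 and 0.94 fit an SD of about 3.6 to 3.7 better than 2.54. The documents do not say which reading was used, so all three are carried forward.

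**2. What a 5% fall in REE_Low can mean.** Set placebo REE_27 = 100 and REE_Low = 117.4. A 5% fall gives 117.4 × 0.95 = 111.53.
- REE_27 unchanged: 100 × (111.53/100 − 1) = 11.5% NST.
- REE_27 also down 5%, to 95: 100 × (111.53/95 − 1) = 17.4% NST. Absolute delta-EE is 111.53 − 95 = 16.53.

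**3. How often a general fall makes REE_Low significant.** The size of the fall is an assumption; NST is intact throughout. Ranges run from SD 3.7 to SD 2.54.

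| Equal fall at both temperatures | alpha 0.05 | alpha 0.0125 |
|---|---|---|
| 5.0% | 0.99 to >0.99 | 0.93 to >0.99 |
| 1.6% | 0.28 to 0.51 | 0.11 to 0.27 |

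If the hypothesis is read as needing an observed mean fall of 5% or more, a true 1.6% fall rarely reaches it. At SD 3.59, z = (5 − 1.6)/(3.59/√12) = 3.28, probability 0.0005. At SD 3.7 it is 0.0007.

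**4. Which form of the contrast.** Under an equal 5% proportional fall, absolute delta-EE itself drops by 17.4 × 0.05 = 0.87, although % NST has not moved. In simulation with session error proportional to level, a test of absolute delta-EE in the direction of reduced NST then gives a false claim with probability 0.07 to 0.11 at alpha 0.05 and 0.02 to 0.03 at alpha 0.0125. The same test on % NST stays at 0.025 and 0.006. So % NST is the safer basis, and it is the first definition in section I.

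**5. Power of the contrast.** No SD is documented for it. With independent session errors its SD is √2 times that of one drug-placebo difference. For a 5-point fall confined to the cold, n = 12:

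| Reading of the SD | Contrast SD | alpha 0.05 | alpha 0.0125 |
|---|---|---|---|
| 2.54 is the paired SD | 3.59 | 0.99 | 0.95 |
| 2.54 is the per-session SD | 5.08 | 0.87 | 0.66 |
| Paired SD is 3.7 | 5.23 | 0.85 | 0.63 |

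These carry over closely to % NST. If errors scale with level, a 5% cold-only fall is 0.05 × 117.4 = 5.87 points and the middle SD becomes about 1.174 × 5.08 = 5.96. The ratio 5.87/5.96 = 0.98 matches 5/5.08 = 0.98.

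If REE_27 also falls 1.6 points, the effect on the contrast is 5 − 1.6 = 3.4, and power is 0.85/0.62 at SD 3.59 or 0.56/0.31 at SD 5.08 (alpha 0.05/0.0125). If shivering leaves 10 or 9 usable men, at contrast SD 5.08, the chance that both REE_Low and the contrast are significant is 0.79/0.52 or 0.73/0.43.

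**The case against.** **The contrast is already there.** This stands. Section II.2 lists the delta-EE comparison and the 27°C drug effect as secondary objectives, and it uses the same verb, reported, for primary results. A reader might infer that the plan lacks the discriminating analysis or demotes it to description; the documents do not support that. What is missing is its role in the NST conclusion.

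**The primary objectives ask about EE in the cold, and REE_Low answers that.** This also stands. A reader might infer that the plan will declare NST inhibition from REE_Low alone, but no section says so. The gap is that nothing rules it out, while the stated aim and the predictions for dantrolene and magnesium are about NST.

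**The general fall is hypothetical.** Largely so. For propranolol, "The effect of 160 mg propranolol at thermoneutrality is expected to be slight", with a proportionally greater effect in the cold. The text says that propranolol's effect on EE "has been studied multiple times, with three examples being a reduction of 4.1"%, then 1.6% and 5.0%. It is tempting to read these as an established thermoneutral fall of up to 5%, but they do not show that. The 4.1% and 1.6% were non-significant. The 4.1% is cited to a study whose title refers to dynamic exercise. The 5.0% is cited to a study that Table 1 lists at 16-22°C. The documents do not give the conditions under which either reduction was measured. For dantrolene, "We are not aware of prior studies of the effect of dantrolene on EE under conditions similar to those in this protocol". For magnesium no EE data are cited.

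**Requiring the contrast could mislead.** Restricting it to men who do not shiver selects on a post-treatment outcome, which section II.1 treats as a drug effect for propranolol and dantrolene. It may remove the men most affected. This stands and shapes the fix.

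**Conclusion.** The point holds in a limited form. For these three drugs a significant fall in REE_Low shows lower EE in the cold. It does not by itself show NST inhibition, because the same 111.5 is compatible with NST of 11.5% or 17.4%. That part is algebra from the protocol's definitions and needs no assumption about variability.

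How much it matters depends on a thermoneutral effect that the documents do not establish. If the general fall is near 5%, REE_Low would almost always be significant with NST intact (0.93 or more at either alpha). If it is near 1.6%, significance is far from certain and an observed 5% fall is very unlikely. The problem is therefore material mainly for a general fall of several percent. These probabilities assume 12 completers, two-sided paired tests and an SD between 2.54 and 3.7; the contrast figures also assume independent sessions.

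The weakness is in the link from result to conclusion, since the sessions already scheduled can answer the question.

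**What to change.** Keep REE_Low as the primary test and keep the shivering rule. Add a statement for propranolol, dantrolene and magnesium:

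- Any conclusion of NST inhibition rests on the drug-versus-placebo contrast in % NST, 100 × (REE_Low/REE_27 − 1), given as an estimate with a confidence interval at the same alpha as the REE_Low test. Show absolute delta-EE and the 27°C drug effect beside it.
- If the interval does not exclude zero in the direction of reduced NST, report a lower REE_Low with NST inhibition not shown.
- Give the number shivering on each drug and on placebo, and read the contrast together with that comparison rather than from the non-shivering men alone.

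**Cost.** No new data or sessions. Cohort 1 enrolment is complete, so the number of men cannot be raised to offset lost power. The change should be labelled a post-enrolment analysis amendment, which the protocol's opening statement on IRB review requires to be approved first. The price is lower power for the NST claim than for REE_Low. The amendment should show the whole range in step 5 of the working, and note that power is lower still if REE_27 also falls or men are lost to shivering. The REE_Low result is unaffected.
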